Pain catastrophizing – Pain catastrophizing will be measured by the Pain Catastrophizing Scale (PCS).⁵³ The PCS is a 13-item self-report scale, with each item rated on a 5-point scale: 0 (Not at all) to 4 (all the time). It is broken into three subscales (magnification, rumination, and helplessness); results from the initial development and validation studies indicate that the PCS is a reliable and valid measurement tool for catastrophizing in clinical and non-clinical populations. PCS will be completed prior to and following completion of the intervention and at the 3- and 6-month follow ups to assess the durability of the intervention.

Depression and Anxiety - To measure symptoms of depression and anxiety, the PROMIS® (Patient-Reported Outcomes Measurement Information System) person-centered measures will be utilized.⁵⁴ Specifically, the 8-item PROMIS depression and anxiety short forms will be compared prior to and following completion of the intervention; to evaluate the stability of CBT skills, the PROMIS will also be administered at 3 and 6 months.

Potential confounders – Pre-existing medical comorbidities or post-operative complications may affect surgical outcomes with respect to pain severity and resolution. To account for the effects of these confounders, all medical comorbidities will be extracted from the EHR by the study coordinator prior to surgery and recorded in the study database. Also added to the study database will be any unanticipated adverse events following surgery, and with medical comorbidities, considered as moderators of the effects of the intervention on the development of CPSP.

Post-operative pain intensity – Severity of post-operative pain will be operationalized as (1) responses on a visual analogue pain scale (VAS) and (2) consumption of opioid analgesic medications during the first 72 hours following surgery. The VAS ranges from 0 (no pain) to 10 (worst pain imaginable), and pain scores are collected every 4 hours as part of routine practice. Pain ratings will be graphed over time and area under the curve calculated. Dose of opioid analgesics consumed during this period (24hr increments and total) will be abstracted from the electronic health record and converted into MEDD for analysis.

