Chronic post-surgical pain – To evaluate for the presence of CPSP, subjects will be asked at 3- and 6-months if they have pain in the surgical site that developed or increased in intensity following the surgery utilizing a checklist based upon the IASP definition of CPSP (Appendix). If they respond affirmatively, BPI pain scores will be collected to assess the intensity and interference associated with the CPSP. In addition, subjects will be asked if they are continuing to use opioids at these timepoints, and if so, daily MEDD calculated for analysis.

2. Group Modifications:

The only group modification with respect to measures is that only those in the intervention group will participate in the survey assessing subject satisfaction with the intervention.

3. Method for Assigning Subjects to Groups:

A randomization scheme will be generated by the study biostatistician and provided to the study coordinator who will assign consecutively enrolled subjects to group.

4. Administration of Surveys and/or Process:

The data collection schedule is described below:

	Baseline (T-4weeks)	Pre-operation (T0)	Post-operation (T = 72hr)	Follow-up (T + 3 and 6 months)
Chronic Pain Intensity (BPI)	X	X		X
Opioid Use (MEDD)	X	X		X
PDMP review	X			X
Pain Catastrophizing (PCS)	X	X		X
Depression & Anxiety symptoms (PROMIS)	X	X		X
CBT use, adherence, satisfaction ^a		X		
Post-operative Pain Severity (72hr VAS)			X	
Post-operative Pain Severity (72hr MEDD)			X	
Chronic post-surgical pain checklist				X

^a subjects in treatment group only

5. Data Management:

Collected data will be entered into the U Penn School of Nursing REDCap (Research Electronic Data Capture) system by trained CITI- and HIPAA-certified research assistants, which is a central and secure resource for data processing and management. As the front-end collection instrument is created, REDCap automatically creates a database designed to store the data that will be recorded from the research. The U Penn School of Nursing has licensed its own version of REDCap that is housed on password protected servers located within a data center inside the School of Nursing firewall, and therefore are afforded the same network protections as other sensitive clinical systems. REDCap was developed specifically around HIPAA-Security guidelines with features such as data encryption and is recommended to Penn researchers by our Office of Human Research.

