Participants will be informed that, other than any effect of the intervention for the treatment group, no direct benefit is expected to accrue to them from participation in the study.

3. Subject Privacy:

Consent and data collection sessions will take place in private rooms where strict privacy is enforced and all staff are HIPAA certified.

4. Subject Confidentiality:

All records will be kept strictly confidential. No one except the researchers will know the subjects are in a research study. Data forms for the collection of health and study data will be coded with each subject's unique identification number. No data form will identify the participants by name. Hardcopies of data forms will be kept in locked files with keys held only by the study investigators. All electronic data will be stored with the password and firewall protected REDCap data collection and management system of the U Penn School of Nursing. No presentation or publication of the results of this study will refer to the individual participants or present information that would identify any participant. All persons working on the proposed work will have completed HIPAA training and the [Collaborative Institutional Training Initiative](#) (CITI) Basic Courses in the Protection of Human Research Subjects and Biomedical Focus Responsible Conduct of Research (RCR) modules.

How will confidentiality of data be maintained? Check all that apply.

XX Paper-based records will be kept in a secure location and only be accessible to personnel involved in the study.

XX Computer-based files will only be made available to personnel involved in the study through the use of access privileges and passwords.

XX Prior to access to any study-related information, personnel will be required to sign statements agreeing to protect the security and confidentiality of identifiable information.

XX Whenever feasible, identifiers will be removed from study-related information.

A Certificate of Confidentiality will be obtained, because the research could place the subject at risk of criminal or civil liability or cause damage to the subject's financial standing, employability, or liability.

A waiver of documentation of consent is being requested, because the only link between the subject and the study would be the consent document and the primary risk is a breach of confidentiality. (This is not an option for FDA-regulated research.)

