Co-principal investigator, [name], PhD, will contribute 1.44 calendar months effort to the project over the two-year project duration. She will be responsible for obtaining IRB approval, directing development of the REDCap database, and overall coordination of the efficacy testing of the intervention. Working closely with Co-I [name], she will monitor subject recruitment and enrollment efforts and verify subject eligibility. She will also oversee the day-to-day activities and performance of the Study Coordinator, and be responsible for monitoring the accuracy, quality and completeness of data collection, ensure protocol fidelity, and compliance with all regulatory and funding agencies. She will direct data analysis, and play a primary role in dissemination of findings and grant writing.

The Co-investigator, [name] will contribute 0.6 calendar months during both years of the project. He will be responsible for working closely with Study Surgeons [name] and [name] to identify and recruit potentially eligible patients for study enrollment. He will work with the Study Coordinator to establish eligibility and obtain informed consent. Importantly, he will serve as the primary liaison to the orthopedic surgeons and the surgery service to ensure effective collaboration as a means to achieve study objectives. In addition, he will assist with data interpretation and the dissemination of findings. [name] will serve the primary study clinician, managing any health-related issues experienced by study subjects during study participation.

Statistician, [name], will contribute .45 calendar months effort to the project during Year 2 only. He will serve as the study statistician, working with the REDCap derived database to the complete the analysis as outlined in the Research Plan. Specifically, he will oversee data cleaning and variable construction, run interim analysis, and complete the descriptive and multivariate analysis required to meet the study specific aims. As results become available, he will work closely with the Co-PIs to refine the analytical plan as needed and contribute to the writing of dissemination materials.

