[name] has private locking office in the Perelman School of Medicine and shared office space in the primary recruitment site, PPMC. At both facilities, his office space is equipped with locked filing cabinets, bookshelves, desk, minimum 4 GHz computer with HP printer, Windows XP service pack 3 operating system, Microsoft Office Professional (Word, Excel, PowerPoint, Access), SPSS or SAS statistical analysis software, and e-mail and internet access. He enjoys full access to the centralized Department of Orthopaedic Surgery database through which patient randomization and data collection will be done.

Study Surgeons [name] and [name] practice in the Department of Orthopaedics (Penn Orthopaedics) which boast a talented and specialized interdisciplinary team of health care providers dedicated to a whole-body approach to diagnosing and treating joint pain. They complete thousands of joint procedures a year (approximately 1100 primary TKAs and 500 TKA revisions), and provide services in sports medicine, cartilage repair, neuro-orthopedics, orthopaedic oncology, and trauma and fracture repair.

The Department of Orthopaedics provides the latest diagnostic techniques and the most advanced surgical and non-surgical options for a range of disorders, injuries and pain found in joints, muscles or bones. Penn Orthopaedics has 49 exam rooms, 4 Operating Rooms for Outpatient Procedures and 2 floors of Physical and Occupational Therapy at Penn Medicine University City. It brings together Penn clinicians from numerous specialties, including orthopaedics, rheumatology, physical medicine and rehabilitation, pain medicine and musculoskeletal radiology. This team-based model of care creates a seamless, integrated patient experience and the most efficient process towards an accurate diagnosis and appropriate treatment plan. Drs. [name] and [name] each have their own 100 square feet offices with computers, printers, internet access and standard furniture.

In addition to clinical space, to support research activities, the Department of Orthopaedic Surgery provides space and resources for Clinical Research staff (up to 10 full time coordinators) associated with these studies. The

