space is located in the department where we have 600 square feet of dedicated space, eleven PCs and eleven desks as well as storage for research binders and other confidential information. Electronic research files are stored on UPenn Health System secured servers behind the UPenn Health System firewall and are additionally protected through the use of limited access folders on the servers. Clinical data is maintained in PennChart which is a Penn-specific image of EPIC Electronic Medical Records Software (Epic Systems Corporation, Madison, Wisconsin).

The project is designed, staffed and budgeted to be successfully completed in 24 months. In consultation with Drs. [name] and [name], [name] will train the study coordinator coach on delivering the opioid taper MI intervention during months 1-3, during which time study start-up activities will take place. Enrollment will begin month 3; at a rate of 12-13 enrollments per month, we anticipate having enrolled 166 subjects (n=150, assuming 10% attrition) by study month 15, providing adequate time for 3- and 6-month follow up, and dissemination activities.

REFERENCES

1. http://aaos-annualmeeting-presskit.org/2018/research-news/sloan_tjr/
2. <https://www.ncbi.nlm.nih.gov/pubmed/17403800>

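### The facilities text runs randomization and data collection through an orthopaedic department database found nowhere in Methods, and gives full access to the co-investigator who reviews eligibility

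*Combined protocol and SAP*

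**What the plan says.** Two parts of the document describe how patients are assigned and where data go.

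- **Methods, item 3 (Method for Assigning Subjects to Groups)** gives its whole rule in one sentence: "A randomization scheme will be generated by the study biostatistician and provided to the study coordinator who will assign consecutively enrolled subjects to group". It names a generator and an assigner, but no system.
- **Methods, item 5 (Data Management)** has collected data entered into the School of Nursing REDCap. **Risk/Benefit Assessment, item 4 (Subject Confidentiality)** is broader: "All electronic data will be stored with the password and firewall protected REDCap".
- **Study Procedures, item 2 (Data Collection)** takes the 72-hour outcomes from the electronic health record, checks opioid use against the prescription monitoring programme, and takes everything else from the patient.
- **Resources Necessary for Human Research Protection**, in the paragraph on the co-investigator's office and computing: "He enjoys full access to the centralized Department of Orthopaedic Surgery database through which patient randomization and data collection will be done". A little further on, the same section places electronic research files on Health System servers.

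On roles, Subject Recruitment and Screening (repeated under Study Procedures) has a co-investigator review eligibility. Resources says the co-investigator works with the coordinator to confirm eligibility and take consent, and is the main link to the surgeons.

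**The concern.** The facilities sentence states what will happen in this trial, and it is the only sentence in the document that names a system for randomization. Nothing in Methods overrides it, because Methods names no system, describes no concealment procedure and sets no limit on access to allocations.

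Allocation concealment is at stake. If a person who confirms eligibility or helps with consent can see the next assignment, that knowledge can influence who is approached, who is judged eligible, or the order in which patients are enrolled. The criteria leave room for judgement, for example on whether bipolar disorder is poorly controlled or whether a condition interferes with consent. Because consecutive enrolments are assigned from the scheme, a change of order is enough to change arm.

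There is also a data-integrity question. With three candidate locations (REDCap, the orthopaedic database and Health System servers), a reader cannot tell which holds the allocation record or which is the system of record for outcomes.

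**Working it through.** No arithmetic applies: the point rests on no rate, effect size, power or alpha. The check compares the sections.

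1. **Is the orthopaedic database part of the Methods?** No. It is absent from the assignment paragraph, Data Management, the data-source paragraph and the coordinator's duties, which have study data entered into REDCap.

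2. **Does it conflict with the storage rule?** Yes. Subject Confidentiality covers all electronic data without exception. A database through which randomization and data collection are done would hold at least the allocation and some study data. The statement about Health System servers adds to the conflict.

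3. **Does it conflict with the biostatistician's scheme?** Not strictly. A scheme produced by the biostatistician could be loaded into a departmental database and applied there by the coordinator. The two statements are unreconciled, but they do not exclude each other.

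4. **Who has the access?** The sentence says he, and names are removed. It follows the paragraph on the co-investigator's appointment in Anesthesiology and Critical Care, so I take him to be that co-investigator, and the same one who reviews eligibility. Resources describes only one co-investigator.

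5. **Does that person influence entry?** Yes, on three counts: reviewing eligibility after the record search, confirming eligibility with the coordinator, and helping to obtain consent.

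6. **Does anything separate entry from allocation?** No such provision appears. The Baseline Study Session gives intervention patients their access and training in the same visit as consent and baseline measures. The text does not say that assignment is released only after those measures are complete.

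7. **Could the analysis repair a loss of concealment?** Only in part. The Statistical Analysis section tests baseline differences and adjusts for variables found imbalanced, which reaches measured variables only. A patient's readiness to taper, for example, is not among the scheduled baseline measures, yet could affect both selection and opioid use.

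Steps 4 to 6 make concealment the main risk. Full access is stated; an ability to view upcoming assignments is inferred from it.

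**The case against.** The strongest reply is that this is one loose sentence in a description of offices and computers. Collection and storage are different steps, so data could be collected through one system and then stored in REDCap. A co-investigator is listed study personnel, so his access alone breaches no disclosure rule. That reply limits the point but does not remove it: randomization is named explicitly, and no other text says where allocation is held or who can see it.

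A reader might also infer four stronger things that the documents do not support.

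- **That the biostatistician's scheme is contradicted.** It is not, because Methods names no system.
- **That arm knowledge will distort the 72-hour outcome**, "consumption of opioid analgesic medications during the first 72 hours following surgery". No section says who prescribes in that period, that this co-investigator does so, or that surgeons or ward staff would see the arm. The name of the primary study clinician, described in the co-investigator's paragraph, is removed. No blinding is promised, and patients can tell clinicians about their coaching, so restricting one database would not remove this risk.
- **That the confidentiality promise is broken**, "No one except the researchers will know the subjects are in a research study". The co-investigator is a researcher, and wider departmental access is not described. Who else can open the database is a fair question, but no breach is shown.
- **That the scheme cannot be produced in time**, because the statistician has "effort to the project during Year 2 only" while "Enrollment will begin month 3". A list is generated once, before enrolment, and Resources describes standing support from the statistics lab that the biostatistician directs.

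**Conclusion.** The point holds as an unresolved conflict that weakens allocation concealment. The conflict with the REDCap storage rule is direct; the mismatches with the assignment paragraph, the data sources and the server statement are matters to reconcile. It rests on two readings: that the person with full access is the co-investigator who reviews eligibility, and that full access to a database used for randomization may include upcoming assignments.

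The documents give no basis for a numerical size. The exposure is potentially every one of the 166 planned enrolments, since all would be assigned through the same mechanism. An influence on 72-hour opioid orders remains a possible secondary risk and should not carry the argument. This is a cheap improvement, to be made before the first randomization because later analysis cannot restore concealment.

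**What to change.** 1. Rewrite the facilities sentence so that the orthopaedic database is not the randomization or data-collection system. If it is used to find candidates, say only that.
2. Name the School of Nursing REDCap project as the system of record for allocation and study data.
3. Have the biostatistician or the statistics lab generate the list and load it into REDCap during start-up, before enrolment begins in month 3.
4. Set user rights so that upcoming assignments are hidden from everyone who screens, confirms eligibility or obtains consent, including the co-investigator and the coordinator. Release each assignment only after consent and baseline measures are recorded. Methods item 3 then needs a matching change, since it now hands the scheme to the coordinator, who also takes consent.
5. Keep a patient's current arm available to the study clinician when it is needed for that patient's safety.
6. Reconcile Methods items 3 and 5, the Data Collection paragraph, Subject Confidentiality and the two statements in Resources (orthopaedic database and Health System servers).

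The cost is a wording correction, a small set-up task in a system the trial already uses, and an access request when the arm is needed. Sample size, visits and analysis do not change.

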Appendix
Chronic Post-Surgical Pain (CPSP) Checklist

If Brief Pain Inventory indicates that patient still has pain:	
1. Did the pain develop or increase in intensity after the surgical procedure?	 YES  NO
2. Is the pain in the same location/area as the surgical procedure?	 YES  NO
3. Is the pain distinct from other kinds of pain that were present prior to the surgery?	 YES  NO  NA
4. Could your pain be described as burning, prickly, tingling, electric shocks and/or pins and needles?	 YES  NO
5. Is the skin covering your painful area more sensitive to touch?	 YES  NO

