A power analysis was conducted for the post-operative pain outcomes; being a novel intervention, opioid taper outcomes were not considered. Estimated group means, variances, and effect-size were drawn from the literature.^{41,42} The sample size estimate was derived for the primary outcome variable, chronic pain severity, using an expected baseline mean of 4.82 (Effect size: 0.33). Based on estimates obtained, a sample size of 75 participants provides 80% power to detect a pre-post improvement in pain severity (14.5%), depression (21.3%), anxiety (24.3%), and catastrophizing (29.5%), statistically significant at alpha of 0.05. Being a novel intervention, the analysis for chronic post-surgical pain will be considered exploratory and used to obtain effect size estimates. We anticipate a low attrition rate (10%) and will over-recruit 16 additional participants (total 83 subjects per group) to retain adequate power.

2. Key Inclusion Criteria:

[figure not shown]

Figure 1. Predictive factors of CPSP following TKA

1. Males and females, age > 21 years
2. Chronic non-malignant pain of at least 3 months duration
3. Morphine equivalent daily dose (MEDD) > 50 milligrams for at least 3 months
4. Able to enroll at least 4 weeks prior to planned surgery
5. Able to speak, read and comprehend in English at the 6th grade or higher proficiency

Participants will be selected so as to represent the gender, ethnicity, and age of the patient population of individuals seeking TKA in greater Philadelphia area, thus the sample is expected to be 50% women, 55% white, 35% African-American, 6-8% Latino, and 2-4% other or multiracial, and on average 67 years of age. No restrictions on gender or ethnicity will be applied. Because total knee arthroplasty surgery is uncommon in children, individuals under the age of 21 will not be included in this proposed study.

3. Key Exclusion Criteria:

1. Pain of malignant origin
2. Current or past history of opioid use disorder (including those on medication-assisted therapy)
3. Revision of TKA
4. Comorbid CNS disease such as dementia, HIV, psychosis, poorly controlled bipolar disorder or any condition interfering with informed consent

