The research will be conducted in the Department of Orthopaedic Surgery at Penn Presbyterian Medical Center, and data analysis will be performed at the Biostatistics * Evaluation * Collaboration * Consultation * Analysis (BECCA) lab at the U Penn School of Nursing.

The duration of subject participation is approximately seven (7) months beginning four (4) weeks prior to surgery and ending following the 6-month data collection time point. The baseline study session will last approximately 30minutes for those in the control group and 60minutes for those in the experimental group. For those in the experimental group, subjects will spend approximately nine (9) hours prior to surgery receiving the intervention. For those in the control group, subjects will spend approximately four (4) hours prior to surgery receiving the standard educational care. Just prior to the surgery, subjects in both groups spend approximately 45minutes providing pre-operative data, and they will additionally spend one (1) hour providing data at the 3- and 6-month follow up at 30minutes each. Thus, the duration of participation for those in the experimental group is approximately 12 hours, and for those in the control group, approximately 7.5 hours.

METHODS:

1. Study Instruments:

Preoperative chronic pain – The severity of preoperative chronic pain will be evaluated with the Brief Pain Inventory (BPI),⁵² along two dimensions: intensity and interference. Pain intensity is rated on a 0 (no pain) to 10 (worst pain imaginable) scale as the worst in the past 24 hours, least in the past 24 hours, average pain and current pain. Pain interference is measured in 7 areas: general activity, mood, walking ability, work, sleep, enjoyment of life and relationships on a 0 (no interference) to 10 (interferes completely) scale. The composite mean of these scores are used as a pain interference score. BPI scores will be collected prior to the intervention and compared to those collected just prior to surgery and at 3- and 6-month follow-up.

Long-term opioid use – Preoperative opioid use will be measured by converting to morphine equivalent daily dose (MEDD) prior to beginning the intervention, during the study visit just prior to surgery and at the 3 and 6 months follow up if the patients are still taking opioids. At each timepoint, state prescription drug monitoring program will be queried as a check on self-reported opioid use.

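### The CPSP checklist does not ask the protocol's own CPSP question: it is not tied to the operated knee, its items are not linked, and its order relative to the BPI is circular

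*Combined protocol and SAP*

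**What the plan says.** The Background adopts a definition of CPSP in which a single pain must meet both an onset condition and a location condition. Methods, Study Instruments (Chronic post-surgical pain) keeps the two together: at 3 and 6 months subjects are asked "if they have pain in the surgical site that developed or increased in intensity following the surgery", using the Appendix checklist.

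The checklist itself is built differently. It opens with "If Brief Pain Inventory indicates that patient still has pain". Item 1 asks "Did the pain develop or increase in intensity after the surgical procedure". Item 2 asks "Is the pain in the same location/area as the surgical procedure". Item 3 asks "Is the pain distinct from other kinds of pain that were present prior to the surgery" and may be answered YES, NO or NA. Neither the form nor the Statistical Analysis section says which answers make a case, or which time before surgery an increase is measured from.

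Study Instruments describes BPI intensity as "worst in the past 24 hours, least in the past 24 hours, average pain and current pain", with no body site. The pain criterion in Key Inclusion Criteria is "Chronic non-malignant pain of at least 3 months duration", also with no site.

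On order, Study Instruments (Chronic post-surgical pain), Subject Follow-up, and Study Procedures (Chronic Post-surgical Pain) all run the checklist first and give the BPI only to patients found to have CPSP. The BPI paragraph of Study Instruments and the data collection schedule list the BPI at 3 and 6 months without that condition.

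**The concern.** Pain at more than one site is foreseeable in this sample. Eligibility does not restrict the site, the Background names pain elsewhere in the body as a CPSP risk factor, and item 3 presupposes other pains before surgery. In such a patient 'the pain' has no fixed meaning on the form, and the two conditions that define CPSP can be answered about different pains, or both about the wrong one. No other planned measure is described as recording pain location, so an ambiguous answer could not be corrected at analysis.

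At stake are the 3- and 6-month CPSP rates in Objective 3. Their analysis is exploratory, but its declared purpose is to supply effect-size estimates for larger studies, and endpoint error distorts exactly those.

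**Working it through.** **1. The plan's own figures.** None is given for CPSP: no assumed difference, power or checklist error rate. The only powered figure is 75 participants for a pre-post change with effect size 0.33. A two-sided paired t-test at alpha 0.05 and 80% power gives n = 74.02, rounded up to 75, so it reproduces. It concerns pre-operative pain severity and is not affected here.

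**2. The form against the definition.** Assume the case rule closest to the definition, YES to items 1 and 2 (the plan states none), and apply it to two patients.

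| Patient at follow-up | By definition | Items answered about different pains | Both items answered about the main pain |
|---|---|---|---|
| Back pain worse and dominant; knee pain improved but residual | Not CPSP | Item 1 YES (back), item 2 YES (knee): counted, wrong | Item 1 YES, item 2 NO: not counted, right |
| Long-standing unchanged back pain dominant; knee pain new | CPSP | Item 1 YES (knee), item 2 YES (knee) only if both items happen to be answered about the knee | Item 1 NO, item 2 NO: missed, wrong |

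The single-pain reading repairs the first row and breaks the second. Both are right only if the pain in question is always the knee pain, and neither the lead-in nor item 1 says so.

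**3. Item 3.** It might screen out the first patient, but it has no stated scoring role and allows NA. Requiring YES could also exclude knee pain that was present before surgery and then increased, which the definition counts as CPSP.

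**4. The order.** Body text: checklist, then BPI if CPSP is present. Appendix: BPI, then checklist if pain is present. Taken together, each instrument waits for the other. Giving the BPI to everyone, as the schedule implies, would break the circle but contradicts the three conditional statements. For a patient whom the Appendix lead-in screens out, the plan does not say that CPSP is recorded as absent.

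**5. Illustrative size.** All rates here are assumptions. With true rate p, sensitivity Se and specificity Sp equal in both arms, observed rate = p × Se + (1 − p) × (1 − Sp), so the observed difference is the true difference × (Se + Sp − 1). Take 48% in controls (within the cited 44% to 53%) and 34% with the intervention, a true difference of 14 points:

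- Se = Sp = 0.95: 48.2% v 35.6%; 14 × 0.90 = 12.6 points.
- Se = Sp = 0.90: 48.4% v 37.2%; 14 × 0.80 = 11.2 points.
- Se = 0.85, Sp = 0.90: 46.0% v 35.5%; 14 × 0.75 = 10.5 points.

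With Se = 1, a true 20-point difference becomes 20 × 0.90 = 18 points at Sp = 0.90 and 20 × 0.80 = 16 points at Sp = 0.80.

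**6. Comparison with sampling error.** At 75 per arm, SE = √(0.48 × 0.52/75 + 0.34 × 0.66/75) = √0.00632 = 0.0795, so the 95% half-width is 1.96 × 7.95 = about 16 points.

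**The case against.** The strongest reply is that 'the pain' is singular throughout, that the natural reading is one pain, that Study Instruments states the linked question, and that a trained coordinator asks it by telephone and can clarify. This stands in part. A careful caller and respondent may get it right, so the form *can* misclassify; the documents do not show that it will. It does not dispose of the point, because the single-pain reading still misses new knee pain in a patient whose main pain is elsewhere.

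The BPI is summarised in the protocol, not reproduced, so the administered version might record a site. That is fair, but nothing in the plan says so. A skipped checklist could also be derived as absent when the BPI shows no pain. That works only if the BPI is given first to everyone, which the body text does not say.

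The losses in step 5 (1.4 to 3.5 points from 14) are small beside a 95% half-width of about 16 points, and the CPSP analysis is exploratory. Both are true and limit the severity. Shrinkage of this kind is a bias, however, and a larger trial planned on the estimate would inherit it.

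A reader might go further and infer that the opioid taper, encouraged in one arm only, makes the errors differ by arm. The documents do not support that. The taper belongs to the month before surgery, whereas item 1 asks about pain arising or worsening after it; no coached taper is described at 3 or 6 months; and nothing gives a direction or size for such an effect.

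**Conclusion.** The point holds as a defect of wording and consistency. The checklist does not ask the question that the Background and Study Instruments define, patients with more than one pain can be misclassified in either direction, item 3 is only a partial and unscored safeguard, and the BPI/checklist order contradicts itself. The harm is confined to the exploratory CPSP rates and effect-size estimates; the powered outcome is not touched.

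The size cannot be derived from the documents. If error rates are equal in both arms, the observed difference shrinks by the factor Se + Sp − 1, which takes an assumed 14 points to between 12.6 and 10.5 over the values tried. A claim of bias for or against one arm is not supported. The change should be made, because it is cheap and ambiguous answers cannot be recovered after the calls.

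**What to change.** At both the 3- and 6-month calls, ask every patient first, independently of the BPI: *Do you have pain in or around the operated knee?* Record NO as CPSP absent and keep the patient in the denominator. If YES:

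- word the remaining items about *this knee pain*;
- state the pre-operative time against which an increase is judged (the BPI is scheduled at baseline and again just before surgery, so the choice must be explicit);
- state which answers define a CPSP case, including how item 3 and its NA option count.

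Then reconcile the order of BPI and checklist across the BPI and CPSP paragraphs of Study Instruments, the data collection schedule, Subject Follow-up, Study Procedures and the Appendix, and say whether the follow-up BPI is for everyone or only for CPSP cases.

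The cost is a reworded five-item form, a REDCap edit, a minor IRB amendment and a few seconds on a call already planned for every patient.
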